%AUC($t_{\text{last}}-\infty$)	percentage of AUC(0-∞) that is due to extrapolation from the last measurable concentration to infinity
ADA	anti-drug antibodies
ADaM	Analysis Data Model
AE	adverse event
AESI	adverse event of special interest
AUC	area under the concentration versus time curve
AUC(0-∞)	area under the concentration versus time curve from time zero to infinity
AUC(0- t_{last})	area under the concentration versus time curve from time zero to time t , where t is the last time point with a measurable concentration
BLQ	below the limit of quantification
CDISC	Clinical Data Interchange Standards Consortium
CL/F	apparent total body clearance of drug calculated after extra-vascular administration
C_{last}	last quantifiable drug concentration
C_{max}	maximum observed drug concentration
CMQ	Customized MedDRA Query
CRU	clinical research unit
CSR	clinical study report
DMP	data management plan
ECG	electrocardiogram
eCRF	electronic case report form
HLT	high level term
ICH	International Council for/Conference on Harmonisation
ISR	injection site reaction
LLOQ	lower limit of quantification
MedDRA	Medical Dictionary for Regulatory Activities
MSSO	Maintenance and Support Services Organization
PK	pharmacokinetic(s)
PT	preferred term
SAE	serious adverse event
SAP	statistical analysis plan
SC	subcutaneous
SD	standard deviation

$t_{1/2}$	half-life associated with the terminal rate constant (λ_z) in non-compartmental analysis
TE ADA	treatment-emergent anti-drug antibodies
TEAE	treatment-emergent adverse event
TFL	table, figure, and listing
t_{\max}	time of maximum observed drug concentration
VAS	visual analog scale
$V_{ss/F}$	apparent volume of distribution at steady state after extra-vascular administration
V_z/F	apparent volume of distribution during the terminal phase after extra-vascular administration
WHODrug	World Health Organization Drug Dictionary

1. INTRODUCTION

This SAP has been developed after review of the clinical study protocol (Final Initial Version dated 01 September 2023).

This SAP describes the planned analysis of the PK, safety, and tolerability data from this study. A detailed description of the planned TFLs to be presented in the CSR is provided in the accompanying TFL shells document.

In general, the analyses are based on information from the protocol, unless they have been modified by agreement with Eli Lilly and Company. A limited amount of information about this study (eg, objectives, study design) is given to help the reader's interpretation.

This SAP must be finalized prior to first participant visit. Additionally, the SAP and TFL shells should be finalized prior to any programming activities commencing.

This SAP supersedes any statistical considerations identified in the protocol; where considerations are substantially different, they will be so identified. If additional analyses are required to supplement the planned analyses described in this SAP, they may be performed and will be identified accordingly in the CSR. Any substantial deviations from this SAP will be agreed with Eli Lilly and Company and identified in the CSR.

This SAP is written with consideration of the recommendations outlined in the ICH E3 guideline *Structure and Content of Clinical Study Reports*, ICH E8 guideline *General Considerations for Clinical Trials*, ICH E9 guideline *Statistical Principles for Clinical Trial*.^{1,2,3}

The document history is presented in [Appendix 1](#).

2. STUDY OBJECTIVES AND ENDPOINTS

Objectives	Endpoints
Primary	
To describe the safety of single SC doses of 250 mg and 500 mg lebrikizumab in healthy Chinese participants	Incidence of TEAEs and SAEs
Secondary	
To evaluate the PK of single SC doses of 250 mg and 500 mg lebrikizumab in healthy Chinese participants	C_{\max} , AUC(0-∞), and AUC(0-t _{last}) of lebrikizumab

Exploratory	
To assess the immunogenicity of single SC doses of 250 mg and 500 mg lebrikizumab in healthy Chinese participants	Incidence of TE ADA

Abbreviations: AUC(0-t_{last}) = area under the concentration versus time curve from time zero to t, where t is the last time point with a measurable concentration; AUC(0-∞) = area under the concentration versus time curve from time zero to infinity; C_{max} = maximum observed drug concentration; PK = pharmacokinetic; SAE = serious adverse event; SC = subcutaneous; TE ADA = treatment-emergent anti-drug antibody; TEAE = treatment-emergent adverse event

3. STUDY DESIGN

This is a Phase 1, participant- and investigator-blinded, randomized, placebo-controlled, single-dose study to investigate the safety, tolerability, and PK of lebrikizumab in healthy Chinese participants.

Approximately 24 healthy Chinese participants who have satisfied the entry criteria and completed all screening assessments will be enrolled to ensure at least 20 evaluable participants complete the study. Due to effect of body weight on PK, enrolment of participants with similar body weights between the cohorts is preferred. Participants will be assigned sequentially into 1 of 2 cohorts, each with 12 participants. Within each cohort, participants will be randomized in a blinded manner to lebrikizumab or placebo. The planned doses are as follows:

- Cohort 1: single 250 mg dose of lebrikizumab or placebo via SC injection (n=12; 10 lebrikizumab, 2 placebo)
- Cohort 2: single 500 mg dose of lebrikizumab or placebo via SC injection (n=12; 10 lebrikizumab, 2 placebo)

The duration of the study is approximately 21 weeks, and will consist of 3 periods:

- Screening period: Day -28 to Day -2
- Inpatient period: Day -1 to Day 8
 - single SC dose on Day 1
- Follow-up period: discharge until Day 120 ± 3 days.

Screening period

All participants will be screened within 28 days prior to enrollment.

Inpatient period

Eligible participants will be admitted to the CRU on Day -1. On Day 1, participants will be randomized, and will receive either lebrikizumab or placebo via SC injection.

Participants may be allowed to leave the CRU after completing assessments on Day 8, or later at the investigator's discretion.

[figure not shown]
Follow-up period

Participants will return for PK and immunogenicity sampling and safety assessments at predefined times up to approximately 120 days postdose.

Safety and tolerability will be assessed through safety laboratory assessments, 12-lead ECGs, vital sign measurements, recording of AEs, and physical examinations.

A schematic of the study design is presented in [Figure 1](#).

Figure 1: Study Design

Abbreviations: CRU = clinical research unit; ED = early discontinuation.

4. BLINDING

This is a randomized participant- and investigator-blind study. All measures possible must be taken to maintain the blind; access to the blinding information will be restricted to authorized personnel as described in the protocol. Staff who prepare the study intervention will not be blinded to treatment allocation.

In case of an emergency, the investigator has the sole responsibility for determining if unblinding of a participant's treatment assignment is warranted for medical management of the event. In such cases, the unblinding is to be conducted according to the protocol.

The **CCI** and Eli Lilly study teams will be unblinded throughout the study.

5. SAMPLE SIZE JUSTIFICATION

Approximately 24 participants will be enrolled in 2 dosing cohorts for at least 20 evaluable participants to complete the study. The sample sizes described are customary for Phase 1

studies evaluating safety and PK parameters and are not powered on the basis of statistical hypothesis testing. Each cohort will comprise approximately 12 participants with a randomization ratio of 5:1 between lebrikizumab and placebo. Participants who discontinue the study before completing may be replaced at the discretion of the sponsor and investigator. The replacement participant can complete the entire study period.

6. STUDY TREATMENTS

The study treatment names, and ordering to be used in the TFLs are presented in [Table 1](#).

Table 1: Presentation of Study Treatments in TFLs

Study Treatment	Order in TFLs
Placebo SC	1
250 mg lebrikizumab SC	2
500 mg lebrikizumab SC	3

Abbreviations: SC = subcutaneous

All TFLs will be based on actual treatments.

7. DEFINITIONS OF POPULATIONS

Any protocol deviations will be considered prior to database lock for their importance and taken into consideration when assigning participants to populations.

7.1. Enrolled Population

The “Enrolled” population will consist of all participants assigned to study intervention, regardless of whether they take any doses, or whether they took the correct treatment. Participants will be analyzed according to the treatment group to which they were assigned.

7.2. Safety Population

The “Safety” population will consist of all enrolled participants randomly assigned to study intervention and who received a dose of study treatment (lebrikizumab or placebo). Participants will be analyzed according to the intervention they actually received.

7.3. Pharmacokinetic Population

The “Pharmacokinetic” population will consist of all enrolled participants who received a full dose of lebrikizumab and have evaluable PK data. Participants will be analyzed according to the intervention they actually received.

8. STATISTICAL METHODOLOGY

8.1. General

Listings will be provided for all data captured in the database. Listings will include all participants assigned to the Enrolled population and include data up to the point of study completion or discontinuation. Participants are generally considered to have completed the study if they complete the scheduled follow-up visit (rather than early discontinuation visit). Any participant who discontinues the study will be identified accordingly in the listings. Summaries will include the participants assigned to the relevant population based on data type.

Data analysis will be performed using CCI [REDACTED]

ADaM datasets will be prepared using CCI [REDACTED]

Where reference is made to 'valid' data, this refers to non-missing data which meet the predetermined criteria (eg, are not flagged for exclusion).

Where reference is made to 'all calculations', this includes, but is not limited to, summary statistics, baseline derivation, and changes from baseline.

All figures will be produced on linear-linear or discrete-linear scales, as applicable, unless specifically stated otherwise.

8.1.1. Calculation of the Summary Statistics

For continuous data the following rules will be applied:

- Missing values will not be imputed, unless specifically stated otherwise.
- Unrounded data will be used in the calculation of summary statistics.
- If the number of participants with valid observations (n) < 3, summary statistics will not be calculated, with the exception of n, minimum, and maximum.
- In general, as early discontinuation data are not associated with any scheduled time point, they will be excluded from all calculations of summary statistics. Exceptions may be made where justified.

For categorical data the following rules will be applied:

- For ordered categorical data (eg, AE severity), all categories between the possible minimum and maximum categories will be included, even if $n = 0$ for a given category.
- For non-ordered categorical data (eg, race), only those categories for which there is at least 1 participant represented will be included; unless specifically stated otherwise.
- Missing values will not be imputed, unless specifically stated otherwise. A ‘missing’ category will be included for any parameter for which information is missing. This will ensure that the population size totals are consistent across different parameters.

8.1.2. Unscheduled Readings

Any value recorded in addition to the original value will be defined as an unscheduled value. As unscheduled values are not associated with any scheduled time point, they will be excluded from all calculations.

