8.2.6.3. Hypersensitivity Reactions

Many drugs, including oral agents and biologic agents, carry the risk of systemic hypersensitivity reactions. If such a reaction occurs, additional data should be provided to the sponsor in the designated CRFs.

Sites should have appropriately trained medical staff and appropriate medical equipment available when study participants are receiving study intervention. It is recommended that participants who experience a systemic hypersensitivity reaction be treated per national and international guidelines.

In the case of a suspected systemic hypersensitivity event, additional blood samples should be collected as described in Section 10.2.2. Laboratory results are provided to the sponsor via the central laboratory.

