8.8. Immunogenicity Assessments

Antibodies to lebrikizumab will be evaluated in blood samples collected from all participants according to the SoA in Section 1.3. Antibodies may be further characterized and/or evaluated for their ability to neutralize the activity of lebrikizumab. To interpret the results of immunogenicity, a venous blood sample will be collected at the same time points to determine the serum concentrations of lebrikizumab. All samples for immunogenicity should be taken predose when applicable and possible.

TE ADA are defined in Section 9.3.4.

Immunogenicity will be assessed by **CCI** [REDACTED]

[REDACTED] Antidrug antibody samples will be stored as per local regulation or IRB/IEC requirements. Samples will be immediately destroyed once lebrikizumab is launched or there is no further request on testing the samples from China authority.

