10.2.1. Blood Sampling Summary

This table summarizes the approximate number of venipunctures and blood volumes for all blood sampling, screening, safety laboratories, and bioanalytical assays during the study.

Purpose	Blood Volume per Sample (mL)	Number of Blood Samples	Total Volume (mL)
Screening tests ^a	18.5	1	18.5
Hematology and chemistry ^a	5.5	11	60.5
Pharmacokinetics	3	13	39
Immunogenicity	10	5	50
Total			168
Total for clinical purposes			170

^a Additional samples may be drawn if needed for safety purposes.

10.2.2. Laboratory Samples to be Obtained at the Time of a Systemic Hypersensitivity Event

Purpose of collecting samples after a systemic hypersensitivity event

The samples listed in this appendix are not collected for acute study participant management. The sponsor will use the laboratory test results from these samples to characterize hypersensitivity events across the clinical development program.

When to collect samples after a systemic hypersensitivity event occurs

Collect the samples listed below if a systemic hypersensitivity event is suspected. The timing should be as designated in the table, assuming the participant has been stabilized.

Obtain follow-up predose samples at the next regularly scheduled laboratory sample collection, ideally prior to the next dose after the event, to assess post-event return-to-baseline values.

a All samples for hypersensitivity testing will be assayed by Lilly-designated laboratory. Results will not be provided to the study site. If samples are not collected or are collected outside the specified time period, this will not be considered a protocol deviation.

Abbreviations: ADA = anti-drug antibodies; IL = interleukin.

What information to record

Record the date and time when the samples are collected.

Allowed additional testing for participant management

The investigator may perform additional tests locally, if clinically indicated, for acute study participant management.

10.3. Appendix 3: Adverse Events and Serious Adverse Events: Definitions and Procedures for Recording, Evaluating, Follow-up, and Reporting

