8.6.9. Immunogenicity Assessments

Immunogenicity data will be listed and frequency tables will be presented if analyzed. The frequency and percentage of participants with pre-existing ADA and with TE ADA will be presented. TE ADA are those that are boosted or induced by exposure to study drug, with a 4-fold increase in titer compared to baseline if ADA were detected at baseline or a titer 2-fold greater than or equal to the minimum required dilution of 1:10 (i.e. $\geq 1:20$) if no ADA were detected at baseline. The distribution of maximum titers will also be tabulated in TE ADA positive participants by treatment.

The frequency and percentage of participants with neutralizing antibodies, if measured, may also be tabulated for participants with TE ADA.

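### Does the SAP's blanket exclusion of unscheduled values wrongly keep event-triggered antibody results out of the TE ADA tables?

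*SAP*

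**What the plan says.** SAP 8.1.2 first defines an unscheduled value as one recorded over and above an original value, and then states: "As unscheduled values are not associated with any scheduled time point, they will be excluded from all calculations". SAP 8.1 leaves the scope of that last phrase open: "this includes, but is not limited to, summary statistics, baseline derivation, and changes from baseline".

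SAP 8.1.1 has a similar rule for early-discontinuation data. It stands among the rules for continuous data, is softened at the start, and reads: "they will be excluded from all calculations of summary statistics. Exceptions may be made where justified". Section 8.1.2 has no such limit or exception.

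SAP 8.6.9 sets the TE ADA thresholds: a titre of at least 1:20 if no antibody was found at baseline, otherwise a 4-fold rise. It adds: "The distribution of maximum titers will also be tabulated in TE ADA positive participants by treatment". It does not say which postdose samples are used.

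On sampling, protocol 8.8 says: "Antibodies to lebrikizumab will be evaluated in blood samples collected from all participants according to the SoA in Section 1.3". Protocol 8.2.6.3 adds: "In the case of a suspected systemic hypersensitivity event, additional blood samples should be collected as described in Section 10.2.2". The abbreviation line in protocol 10.2.2 reads "Abbreviations: ADA = anti-drug antibodies; IL = interleukin", and that section also says: "Obtain follow-up predose samples at the next regularly scheduled laboratory sample collection".

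**The concern.** Having no scheduled time point is a good reason to leave a value out of a by-visit mean. It is a weaker reason for a result with no visit column. TE ADA status and maximum titre are per-participant results over the whole postdose period, and a maximum that skips a higher valid titre is not strictly a maximum.

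The omission would not fall at random either. It would fall on participants with a suspected hypersensitivity reaction, which is an event of special interest and the setting in which antibody status is most informative. Protocol 9.3.4 allows for relating antibodies to safety. If an event sample were the only positive one, the study report could list a positive participant whom its table counts as negative. With so few cases expected, that participant could be the whole TE ADA count.

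**Working it through.** The plan states no figure to reproduce. The check is a reading of the text, followed by a size estimate.

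**1. Does the 8.1.2 definition cover an event sample?** The defining sentence describes a value additional to an original one, which fits a repeat blood pressure or a repeated laboratory test. A stand-alone event sample has no original value. The sentence that follows gives a reason (no scheduled time point) that would also suit an event sample, so the text is ambiguous. It does not clearly exclude the sample.

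**2. Are event samples meant to feed the endpoint?**

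| Place | What it indicates |
|---|---|
| Protocol 8.8 | Antibody evaluation uses samples on the schedule of activities |
| Protocol 10.2.1 | Five immunogenicity samples are budgeted |
| Protocol 10.2.2 | Event samples serve to describe hypersensitivity across the whole programme; failing to collect them, or collecting them late, is not a protocol deviation |
| Protocol 9.3.4, SAP 8.6.9 | The TE ADA definition names no sample source |

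The first three rows favour scheduled samples and the last is silent. That event samples are tested for antibodies at all is inferred from the abbreviation line in 10.2.2; the body of that table is not in the text available for this review. SAP 8.6.8 does not settle the matter, because the follow-up data it lists are history, alternative causes and symptoms.

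**3. What would change if the result were left out?** The titres here are assumed, for a participant with no antibody at baseline.

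- Negative at every scheduled draw, 1:80 at an event sample: TE ADA negative if the sample is excluded; positive with maximum 1:80 if it is included. A dose group goes from 0/10 = 0% to 1/10 = 10%; the two groups together go from 0/20 = 0% to 1/20 = 5%.
- Scheduled 1:20, event sample 1:160: positive either way; only the tabulated maximum differs.

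Baseline is unaffected, since SAP 8.1.3 already uses the last scheduled predose value.

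**4. How likely is it?** Inputs: 10 participants on lebrikizumab per cohort, 20 in total (protocol 4.1); TE ADA rate p of 4.2% to 5.0% in a completed healthy-participant study (protocol 2.2).

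- Expected cases per dose group: 10 × 0.042 = 0.42 to 10 × 0.05 = 0.50.
- Expected cases in total: 20 × 0.042 = 0.84 to 20 × 0.05 = 1.0.
- Chance of at least one case, 1 − (1 − p)^20: 57.6% to 64.2%.

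These figures count all TE ADA cases, not the ones lost. To be lost, a case must follow a suspected reaction, have an event sample tested for antibodies and entered in the study database, meet the threshold there, miss it at every scheduled draw, and then be handled by the literal reading of 8.1.2. The documents give no rate for this. Assume that a share s of TE ADA cases, 1% to 10%, is positive only at an event sample:

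- Expected loss = expected cases × s: 0.84 × 0.01 = 0.008 to 1.0 × 0.10 = 0.10 participants.

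**The case for a change.** The strongest case for a change is that it costs two or three sentences and no data. The wording of 8.1.2 is absolute, 8.1 widens it, and the softer rule in 8.1.1 shows that the authors knew how to allow exceptions. SAP Section 4 leaves the sponsor's study team unblinded throughout, so a decision taken after a positive event sample appeared would be post hoc. Scheduled draws are also sparse. Days 1 to 120 span 119 days, so the mean spacing is 119/4 = 29.8 days with four postdose draws (protocol 10.2.1) or 119/5 = 23.8 days with five (the schedule row, whose column alignment is imperfect). A short-lived response could fall between draws.

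Part of this stands. The SAP does not say which samples count, and the literal reading is possible. The rest carries less weight. The mean spacing says little, because the draws are unevenly spaced. A response that persists should be seen at a later scheduled draw, and the early-discontinuation visit appears to include an antibody sample. The post hoc worry matters little where nothing is tested and any disputed case would be one identifiable participant whose results can be set out in full.

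The proposed cure also has a cost. Participants with reactions would get extra draws and so extra chances to be classed positive. That would build an association between antibodies and hypersensitivity into the counting rule, and a second, scheduled-only count would be needed to show its effect.

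**Conclusion.** No change to the plan is needed. There is a gap in detail: SAP 8.6.9 does not name the samples behind TE ADA status and maximum titre. An analyst can fill it sensibly from protocol 8.8 and from the purpose given to event samples in 10.2.2. The likely result, scheduled samples only, is a fair trade-off: it may miss a rare positive, but it keeps ascertainment equal across participants.

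The worst single case is 10 percentage points in one dose group or 5 points over both. The expected loss is 0.008 to 0.10 participants. That range rests on the earlier healthy-participant TE ADA rate applying here and on the assumed 1% to 10% share, which has no source in the documents. Even the upper end concerns an exploratory endpoint with no hypothesis test, whose tables appear only if the data are analysed. SAP 8.1 lists all data captured in the database, so an event result held there would remain visible to the reader of the report. Whether event assay results do enter the database is not stated.
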